9. POTENTIAL RISKS AND CHALLENGES

A major risk to the DeWorm3 Project is low treatment coverage and/or adherence. Low coverage could be a result of failure to access sufficient proportions of the population, large rates of population migration, or suboptimal adherence (i.e. participants do not consume the drugs they are given). Other potential challenges include political instability, the presence of transmission hotspots in areas with low coverage, and unprogrammed MDA activities in either trial arm. In addition, while STH resistance to benzimidazole anthelmintics has not been documented in humans, it is known to occur in animals and could pose a risk to the success of transmission interruption.

10. TIMELINE

	July-Dec 2016	Jan-June 2017	July-Dec 2017	Jan-June 2018	July-Dec 2018	Jan-June 2019	July-Dec 2019	Jan-June 2020	July-Dec 2020	Jan-June 2021	July-Dec 2021	Jan-June 2022	July-Dec 2022	Jan-June 2023	July-Dec 2023
IRB approvals															
CRF development															
Database development															
SOP development															
Baseline census															
Cluster randomisation															
MDA															
Interim Analysis to feed models															
Surveillance															
Data cleaning															
Data analysis															
Manuscript prep and publications															

## 2. INTRODUCTION

### 2.1 BACKGROUND AND RATIONALE

Soil-transmitted helminths (STH) are group of intestinal parasites (*Ascaris lumbricoides*, *Ancylostoma duodenale*, *Necator americanus* and *Trichuris trichiura*). These parasites infect an estimated 1.45 billion people globally, resulting in the loss of almost 5 million disability adjusted life years (DALYs) annually [1, 2]. High to moderate intensity STH infections are associated with increased risk of malnutrition, iron-deficiency anemia and other adverse physical and cognitive morbidities, particularly in children. The current World Health Organization (WHO) strategy for controlling STH is based on mass drug administration (MDA) of albendazole or mebendazole to pre-school and school-age children, women of childbearing age (including pregnant women in the second and third trimesters and breastfeeding women) and adults in certain high-risk occupations such as agricultural laborers or miners, with the goal of eliminating STH-related morbidity [3-5]. While the current strategy of MDA for STH control has proven successful in controlling morbidity, the incidence of reinfection post-treatment is high and targeted MDA is unlikely to break transmission of STH in many settings [6]. This is in large part due to adult reservoirs of disease [7, 8]. Even if coverage of all targeted populations were optimized, the current STH strategy would likely need to be continued until significant economic development and universal water, sanitation and hygiene (WASH) access are able to interrupt transmission [9]. As a result, there is increased interest in alternative approaches to interrupt STH transmission using broadly administered MDA strategies targeting all age groups [10], which a recent systematic review and meta-analysis showed are more effective in reducing the prevalence of STH infection [11].

## 2.2. OBJECTIVES

DeWorm3 GENERAL OBJECTIVE: To determine the feasibility of interrupting the transmission of STH (*A. lumbricoides*, *A. duodenale*, *N. americanus* and *T. trichiura*) in focal geographic areas in Africa and Asia by expanding the population targeted and the frequency of delivery of MDA with albendazole.

### 2.2.1 PRIMARY OBJECTIVES

In focal geographic areas in India, Malawi and Benin, where LF programmes have delivered at least five rounds of MDA with albendazole (plus ivermectin or DEC);

#### Objective 1.1

**To compare the prevalence of the predominant STH species (*A. lumbricoides*, *A. duodenale*, *N. americanus* or *T. trichiura*) as measured by quantitative PCR, 24 months after stopping MDA, between clusters randomized to receive twice-yearly community-wide MDA versus clusters randomized to receive standard of care pre-SAC and SAC targeted MDA.**

*Hypothesis: In settings where the prevalence and intensity of STH infections have been reduced through annual MDA of albendazole delivered by LF elimination programs, an additional three years of twice-yearly community-wide MDA with albendazole will result in a lower final cross-sectional prevalence of the predominant STH species driving local transmission as compared to a strategy of pre-SAC and SAC targeted MDA.*

#### Objective 1.2

**To determine whether the transmission of the predominant STH species (*A. lumbricoides*, *A. duodenale*, *N. americanus* or *T. trichiura*) can be interrupted using MDA with albendazole.**

Transmission interruption will be assessed at the cluster level and is defined as reaching a weighted point prevalence of  $\leq 2\%$  of that species as measured by quantitative PCR 24 months after stopping MDA. The proportion of clusters randomized to twice-yearly community-wide MDA versus standard of care pre-SAC and SAC-targeted MDA that interrupt transmission will be compared.

*Hypothesis: In settings where the prevalence and intensity of STH infections have been reduced through annual MDA of albendazole delivered by Lymphatic filariasis elimination programs, an additional three years of twice-yearly community-wide MDA with albendazole will be sufficient to interrupt transmission of the predominant STH species driving transmission at a particular study site, whereas MDA targeting pre-SAC and SAC will not achieve interruption of STH transmission.*

### 2.2.2 SECONDARY OBJECTIVES

#### Objective 2.1

**To compare the prevalence of all STH species (*A. lumbricoides*, *A. duodenale*, *N. americanus* and *T. trichiura*) in clusters receiving either twice-yearly community-wide MDA or standard of care pre-SAC and SAC targeted MDA.**

*Hypothesis: In settings where the prevalence and intensity of STH infections have been reduced through annual MDA of albendazole delivered by LF elimination programs an additional three years of community-wide MDA of albendazole will result in a lower final cross-sectional prevalence of all STH species combined as compared to a strategy of pre-SAC and SAC targeted MDA.*

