Hypothesis: In settings where the prevalence and intensity of STH infections have been reduced through annual MDA of albendazole delivered by LF elimination programs an additional three years of community-wide MDA of albendazole will be sufficient to interrupt transmission of each individual species, whereas MDA targeting pre-SAC and SAC will not achieve interruption of species-specific transmission.

2.2.2 To compare the proportion of clusters in each of the randomisation arms that interrupt transmission, defined as reaching a cluster prevalence of $\leq 2\%$ for each STH species (*A. lumbricoides*, *A. duodenale*, *N. americanus* and *T. trichiura*) by quantitative PCR measured 24 months after stopping MDA.

Hypothesis: In settings where the prevalence and intensity of STH infections have been reduced through annual MDA of albendazole delivered by LF elimination programs, an additional three years of twice-yearly community-wide MDA with albendazole will result in a greater proportion of clusters achieving elimination of all STH species as compared to a strategy of pre-SAC and SAC targeted MDA measure by qPCR 24 months after stopping MDA with albendazole. Reductions in prevalence will be driven primarily by reductions in the predominant species of STH in each geographic area (usually hookworm species), as documented at the baseline assessment.

2.2.3 To compare the combined prevalence of all STH species detected by quantitative PCR 24 months following the last round of MDA in children under 5 years of age residing in clusters receiving twice-yearly community-wide MDA versus those residing in clusters receiving standard of care pre-SAC and SAC targeted MDA.

Hypothesis: Detection of infection in children under 5 years of age 24 months following the last round of MDA is a proxy marker of continued transmission in the community. In settings where the prevalence and intensity of STH infections have been reduced through annual MDA of albendazole delivered by LF elimination programmes, an additional three years of twice-yearly community-wide MDA will result in significantly fewer STH infections occurring in young children, as compared to the number of infections in young children exposed to pre-SAC and SAC targeted MDA.

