7. STATISTICAL ANALYSIS PLAN

All analyses will be conducted separately for each site, unless otherwise specified.

Primary objectives

The effect of the primary exposure on endline infection with the predominant STH species driving transmission in each site (Objective 2.1.1) will be analysed using generalized estimating equations with binomial family and exchangeable correlation matrix. The primary exposure variable will be randomisation arm, while the primary outcome will be individual-level STH infection status (positive or negative for the dominant species driving transmission species by qPCR). Models may be adjusted for baseline cluster-level STH prevalence and urban/rural designation, socioeconomic status (SES), water sanitation and hygiene (WASH) access, age, gender of the participant, household size, or other relevant variables as appropriate. In the primary analysis, these data will be analysed separately by site, while a secondary analysis will pool all data and test for effect modification using an interaction term between study site and randomisation arm.

Transmission interruption in a cluster (Objective 2.1.2) will be defined as achieving a cluster prevalence $\leq 2\%$ of the dominant STH species driving transmission at each site by qPCR 24 months after the final round of MDA. The effect of the primary exposure on the proportion of clusters in which transmission is successfully interrupted will be calculated by comparing the proportion of clusters in each arm in which transmission is successfully interrupted using a chi-squared test.

Secondary objectives

The effect of randomisation arm on endline infection with each individual species of STH (2.2.1), on the proportion of clusters interrupting transmission of each individual species (2.2.2), on endline infection with any STH species among children (2.2.2) and on shedding of fertilized *Ascaris* eggs (2.2.3) will be analysed using generalized estimating equations with binomial family and exchangeable correlation matrix or chi-squared tests, as detailed above. Models may be adjusted for baseline cluster-level STH prevalence and urban/rural designation, SES, WASH access, age, gender of the participant, household size, or other relevant variables as appropriate.

Secondary analyses

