## SECTION 6: ANALYSIS

### 6.1 OUTCOME DEFINITIONS

The outcomes will be a) individual-level STH infection, defined as an individual's test result for the predominant STH (Objective 1.1) or any STH (Objective 2.1), and b) cluster-level transmission interruption, defined as a prevalence of the predominant STH species (Objective 1.2) or each STH species prevalent at baseline (Objective 2.2) of  $\leq 2\%$  with 95% confidence using a one-sided binomial test, as measured by qPCR 24 months after the final round of MDA.

We will classify each individual's infection status as negative (no amplification, Cycle threshold  $>40$ ), positive, or indeterminate; primary analyses will consider indeterminate results negative, while sensitivity analyses will recategorize indeterminate results as positive. Cycle thresholds indicating a positive or indeterminate result for each species will be defined and standardized by the DeWorm3 STH Molecular Support Unit.

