### 6.2.2 Analysis of secondary objectives

The effect of randomization arm on endline prevalence of infection with any species of STH prevalent at baseline (2.1) will be analyzed using generalized estimating equations with Poisson family, robust variance and exchangeable correlation matrix and adjusted for individual-, household-, and cluster-level factors in Table 5 as detailed above. The effect of randomization arm on the proportion of clusters interrupting transmission of each STH species present at baseline (2.2), will be calculated by comparing the proportion of clusters in each arm in which transmission of each STH is successfully interrupted using a Fisher's exact test as detailed above.

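### The SAP drops the protocol's infection comparison for each STH species; other species are left with a 2%-threshold cluster test that has low power unless the arms straddle 2%

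*SAP*

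**What the plan says.** Protocol section 7, under secondary objectives, lists "The effect of randomisation arm on endline infection with each individual species of STH (2.2.1") as one outcome and the proportion of clusters interrupting transmission of each species as another. The methods given for the whole list are "generalized estimating equations with binomial family and exchangeable correlation matrix or chi-squared tests, as detailed above". Because the cluster proportions are listed separately, the first item reads as an individual-level infection comparison, one per species.

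In the SAP, the Objective 2.1 hypothesis (section 2.2.2) is that community-wide MDA "will result in a lower final cross-sectional prevalence of all STH species combined as compared to a strategy of pre-SAC and SAC targeted MDA". Section 6.1 defines the individual-level outcome as the "test result for the predominant STH (Objective 1.1) or any STH (Objective 2.1"), and section 6.2.2 fits one Poisson GEE for Objective 2.1. Non-predominant species appear singly only under Objective 2.2, which is analysed by "comparing the proportion of clusters in each arm in which transmission of each STH is successfully interrupted using a Fisher's exact test". Section 6.1 calls a cluster interrupted when prevalence is at or below 2% with 95% confidence by a one-sided binomial test. The SAP does not say why the species-level infection models were left out.

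**The concern.** The combined outcome cannot do the work of the comparisons it replaces. The protocol itself expects this, in the hypothesis to objective 2.2.2: "Reductions in prevalence will be driven primarily by reductions in the predominant species of STH in each geographic area". If one species carries most of the infections, the any-STH contrast follows that species whatever the others do.

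The per-species test that remains reduces about 1,000 individual results per cluster to a yes or no, and then compares 20 with 20. If a second species sits on the same side of the threshold in both arms, a real difference between arms can leave almost no trace in that count. A site could then report lower prevalence of all STH combined and have little to say about a second species, although the qPCR results are already classified by species. The general objective names all four species.

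**Working it through.** **Inputs.** From the documents: 20 clusters per arm; 1,000 people per cluster at endline (SAP 3.3); ICC 0.003 to 0.005; two-sided α 0.05; predominant species at 7–10% in control and 2% in intervention (SAP 3.3.1); the one-sided binomial rule (SAP 6.1). Assumed: all second-species prevalences, the same ICC for the second species (the documents give neither), and independence between species. Covariates, age and gender weighting and the finite population correction are left out.

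**1. The plan's own figure.** The SAP formula is c = 1 + (z_α/2 + z_β)² [π0(1−π0) + π1(1−π1)][1 + (m−1)ρ] / [m(π0−π1)²]. Take π1 = 2%, π0 = 3.11%, m = 1,000, ρ = 0.005 and 80% power:
- (1.960 + 0.842)² = 7.85
- variance sum 0.0301 + 0.0196 = 0.0497
- design effect 1 + 999 × 0.005 = 5.995
- c = 1 + 7.85 × 0.0497 × 5.995 / (1,000 × 0.0111²) ≈ 20

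Over the eight combinations of c (15, 20), m (500, 1,000) and ρ (0.003, 0.005), the detectable π0 runs from 2.89% to 3.44%. This agrees with the stated 3% to 3.5%.

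**2. The combined outcome.** Any-STH prevalence = 1 − (1−a)(1−b), with the predominant species at 7% v 2%.
- Second species 1% in both arms: 1 − 0.93 × 0.99 = 7.93% v 1 − 0.98 × 0.99 = 2.98%. Power about 100%.
- Second species doubles, 1% to 2%: 7.93% v 1 − 0.98 × 0.98 = 3.96%, ratio 0.50. Power still about 100%.
- Reverse case, predominant species unchanged at 7% and second species halved from 1% to 0.5%: 7.93% v 7.47%. Power 10–13%, against 64–81% for a model of that species alone.

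**3. The per-species tests.** With n = 1,000 and a true 2%, P(X ≤ 12) = 0.038 and P(X ≤ 13) = 0.064, so a cluster passes with at most 12 positives. Cluster counts were simulated as beta-binomial. The species-specific comparison is a two-sample t-test on cluster prevalences, or the formula above inverted for power; both stand in for the GEE. Ranges cover ICC 0.003 to 0.005.

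| Second species, control v intervention | Species-specific comparison | Fisher, one-sided rule |
|---|---|---|
| 1.0% v 0.4% | 84–95% | 36–46% |
| 1.5% v 0.7% | 87–97% | 61–78% |
| 2.5% v 1.0% | over 99% | 95–99% |
| 3.0% v 1.5% | 98–99.9% | 80–87% |
| 4.0% v 2.0% | over 99% | 38–58% |
| 6.0% v 3.0% | about 100% | 0–1% |

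Hand check of the first row at ICC 0.005: variance = (0.0099 + 0.0040) × 5.995 / 1,000 = 8.32 × 10⁻⁵; √(19 × 0.006² / 8.32 × 10⁻⁵) = 2.87; 2.87 − 1.96 = 0.91, giving 82% power. This is close to the simulated 84%.

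The pattern follows from the share of clusters that pass. At a mean of 1% about 70% pass, at 2.5% about 8–14%, at 3% about 3–6%, and at 6% none. Fisher's test sees a large contrast only when the two arms fall on either side of the line.

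**4. A larger ICC.** At ICC 0.01, power for 1.0% v 0.4% is about 61% for the species-specific comparison and 24% for Fisher's test. At 0.02 it is about 40% and 18%. The ordering is unchanged.

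**The case against.** The strongest reply is that the trial is about interruption. Protocol objective 2.2.1 asks whether each species reaches 2% or less; it does not ask for a comparison of prevalence. SAP Objective 2.2 keeps the interruption question for every species. A species averaging 1.0% v 0.4% is below the threshold in both arms, so on the trial's own endpoint there is little to find. Only one sentence of protocol section 7 supports the infection comparison, and the objective numbers in that sentence are out of step with the objectives list. Extra models also add secondary p-values at an unadjusted 0.05.

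Much of this stands. It limits the point but does not remove it: the SAP treats prevalence as informative in its own right for the predominant species (Objective 1.1), and gives no reason to stop there.

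Four stronger readings are tempting, and the documents do not support them.
- A reader might infer that the per-species Fisher test is weak in general. It is not: when the arms straddle 2% it has 80–99% power in the cases shown.
- A reader might classify clusters by point prevalence alone (at most 20 in 1,000), as the shorter wording in SAP 6.2.1 allows. Power for 1.0% v 0.4% then falls to 1–3%. The outcome definition in SAP 6.1 uses the one-sided rule, so that figure should not carry the argument.
- A reader might call a significant any-STH result wrong when only the predominant species fell. It is correct for its combined hypothesis; the risk lies in reading it as evidence about each species.
- A reader might expect the restored models to guarantee 84–95% power. That range depends on an ICC the documents do not give for other species.

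**Conclusion.** The point holds in a limited form. The SAP omits, without explanation, a species-level infection comparison that the protocol's analysis section plans, and neither remaining analysis fully replaces it. Where one species dominates, the any-STH model says little about the rest. If two species are about equally common, neither alone decides it. The Fisher test loses most when both arms lie on the same side of the threshold: 36–46% v 84–95% power for 1.0% v 0.4%, and 0–1% v about 100% for 6% v 3%. In no scenario examined at ICC 0.003 to 0.005 did it beat the species-specific comparison. The sizes rest on assumed second-species prevalences, a borrowed ICC and unadjusted stand-ins for the GEE. This is a cheap improvement to secondary analyses; it does not call the primary objectives into question.

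**What to change.** In SAP 6.2.2:
- Fit the Objective 1.1 Poisson GEE separately to each species prevalent at the site at baseline. Report prevalence ratios with confidence intervals, labelled secondary.
- Keep the any-STH model as a summary, and state that its result is not evidence about non-predominant species.
- Keep Fisher's test for the interruption proportions.

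If the sponsor prefers not to restore the models, the SAP should say why they were dropped.

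The cost is SAP wording and up to three more runs of a specified model per site (at most nine over three sites), with no new data or samples. The downside is a few more secondary estimates at an unadjusted 0.05, which is why the emphasis should be on intervals.

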#### Objective 2.2

**To compare the proportion of clusters in each of the randomization arms that interrupt transmission, defined as reaching a cluster prevalence of  $\leq 2\%$  for all STH species (*A. lumbricoides*, *A. duodenale*, *N. americanus* and *T. trichiura*) by quantitative PCR measured 24 months after stopping MDA.**

*Hypothesis: In settings where the prevalence and intensity of STH infections have been reduced through annual MDA of albendazole delivered by LF elimination programs, an additional three years of twice-yearly community-wide MDA with albendazole will result in a greater proportion of clusters achieving elimination of each STH species prevalent at baseline as compared to a strategy of pre-SAC and SAC targeted MDA measure by qPCR 24 months after stopping MDA with albendazole.*

### 3. STUDY METHODS

#### 3.1 TRIAL DESIGN

DeWorm3 is a multi-site community cluster randomized trial conducted in focal geographic areas in Benin, India and Malawi. At each site, 40 clusters are randomized to receive either three years of twice-annual community-wide mass drug administration (MDA) with albendazole, targeting all age groups, or the current standard of care targeted MDA strategy at the site (Table 1).

#### 3.2 RANDOMIZATION

Within each DeWorm3 study area, clusters will be randomly assigned in a 1:1 allocation ratio to either community-wide or standard of care MDA (Table 1). Restricted randomization will be performed to ensure balance of baseline factors by arm within each country, and stratified by region in India (Jawadhu Hills, n=8 vs. Thimiri, n=32).

